According to the CO@h standard operating procedures (SOP),² individuals eligible for onboarding (ie enrolment in the programme) are those diagnosed with COVID-19, either clinically or via a positive test result, who are symptomatic and (i) either 65 years of age or over, or (ii) clinically extremely vulnerable (CEV) to COVID-19. The model of CO@h delivery is primarily implemented in primary care; referrals may additionally be received from the NHS111 COVID Clinical Assessment Service, NHS Test and Trace, and Accident & Emergency (A&E) hospital departments. Patients are encouraged to record three oximeter readings a day; patients should receive text or email prompts or check-in calls to confirm that they are using

the oximeter correctly and that the readings are 95% peripheral oxygen saturation (SpO2) or above. If patients do not show signs of health deterioration within 14 days of onset of symptoms, they are discharged from the programme.

It is estimated that 4% of the population in England are CEV,³ and that approximately 2.4% of the population are CEV and 65 years of age or under. Patients are normally added to the CEV COVID-19 list through an automated process, based on information from patient records. However, GPs are required to periodically review the list to identify registered patients to be added to or removed from it and hospital specialists may also identify additional patients at high risk of health complications from COVID-19. Therefore, clinical judgement may also influence the process, bringing into consideration multiple additional COVID-19 risk factors.

CO@h is also available to care home residents. Training and support for using pulse oximetry is available and there is a CO@h diary (for recording oxygen saturation levels) that has been tailored for care home usage.

At the beginning of February 2021, the CO@h Programme Board recommended to the National Incidence and Response Board (NIRB) to extend the age criteria for CO@h to people aged 50 and over and place more emphasis on clinical judgement. Anecdotally, some areas were already doing this.

Other related interventions

Vaccinations

The roll-out of COVID-19 vaccinations in England started on 8 December 2020. The order of priority for vaccination is, as of 11 February 2021 (with the four highest priority groups being offered a first vaccination by mid-February 2021):^{4,5}

1. Residents in a care home for older adults and their carers

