- **CO@h offboarding data** – these data will be used to check that our proposed 28-day follow-up period adequately captures the duration of CO@h use (which is intended to usually last up to 14 days from first symptoms, according to the SOP). The various quality issues affecting the onboarding data also affect this data set.
- **Hospital Episode Statistics (HES)** – this data set will include information on hospital admissions and critical care spells.

* Although we will estimate the intervention effect at age 65, we will require data on either side of the threshold to do so. The range or window of ages required will be determined using data-driven methods, but it is expected that 50–79 will be a large enough range not to restrict this choice prematurely.

- **Emergency Care Data Set (ECDS)** – this will be used to provide information on A&E attendances.
- **Office for National Statistics (ONS) mortality data** – this data set will include the registered date of death of any patients that died during the study period.
- **Data used to flag care home residents** – based on patient registration information derived from pseudonymised National Health Application and Infrastructure Services (NHAIS) data.

We will also receive information from Kent, Surrey & Sussex Academic Health Science Network (AHSN) on when each CCG began to implement CO@h and when they were considered ‘fully operational’ (see the later section on Study period, index dates and follow-up period). We will also access publicly available data that maps GP practices to CCGs at the earliest date of study start.

If onboarding data are delayed or unavailable, we may receive aggregate data on number of onboarded patients by CCG. This would allow us to determine whether areas are implementing CO@h at a scale sufficient to potentially identify an effect based on a ‘sharp’ RDD, whereby a treatment assignment effect is estimated (see later section on Statistical methods for more detail).

Study cohort

The study cohort consists of patients in England with a first COVID-19 positive test that were aged 50–79 at the time of test, with the following patient-level and area-level exclusions.

Patient-level exclusions:

- Patients with unlinked records
- Patients who are not captured in the GDPDR
- Patients with missing age or sex information
- Patients onboarded onto CO@h who do not have a first COVID-positive test
- Patients who are CEV
- Potential additional exclusion: patients living in care homes

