Although CEV patients are an important target group for CO@h and may particularly benefit from it, the current study relies on a discontinuity in treatment status by age. As the intention of CO@h is to enrol all CEV patients, it is likely there will be no discontinuity to exploit for this group. Although the fuzzy RDD allows for there to be a proportion of ‘non-compliers’ (ie where patients’ receipt of the intervention contradicts their eligibility due to age), it relies on the assumption that ‘treatment eligibility’ jumps from 0 to 1 at the threshold. For CEV patients, eligibility for CO@h is 1 across all ages. Furthermore, including CEV patients under 65 years of age as non-compliers would bias the resulting estimation of the treatment effect, as they are a cohort with specific baseline characteristics which are predictive of outcomes.

It is estimated that 4% of the general population are CEV.³ We will check the proportion of CEV patients in our data set by age and onboarding status before we exclude them. A discontinuity in CEV patients about the threshold would imply that eligibility criteria are not being followed closely by the NHS clinicians responsible for onboarding patients.

The rationale for the exclusion of CEV patients also applies to patients living in care homes, where a large proportion of care home residents under 65 years of age may also be CEV. Care home residents will therefore be checked by age and onboarding status and, if no age-related discontinuity is identified, will also be excluded from the analysis.

As our study cohort is based on patients being followed for 28 days following a first COVID-19 positive test result, any patients who were onboarded onto CO@h without a COVID-19 positive test will automatically be excluded.

Patients are assigned to a CCG based on their registered GP practice. Area-level exclusions based on CCGs or areas within CCGs include:

- Patients in CCGs that did not implement CO@h or were not fully operational (ie available to all primary care networks (PCNs) in the area) within the study period.
- Patients within particular areas of CCGs that were not offering CO@h during the study period. As CO@h is not a mandatory programme, it may not be rolled out across the whole CCG. If and where we have relevant and reliable data from the AHSN on which areas within a CCG have implemented CO@h, we will limit the analysis to these areas.

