4. **Check that CEV and care home patients should be excluded.** We will also check for an age-related discontinuity in onboarding of CEV and care home residents and exclude these patients from the analysis if there is no discontinuity to exploit at age 65:
 - CEV (yes/no)
 - Care home residents (yes/no)

Window selection

Although we expect there to be a trend in the proportion of patients with certain characteristics by age (eg multimorbidity, diabetes), the local randomisation approach assumes there is a window around the threshold where there are no statistically significant differences between treated and control patients. The symmetric window around the threshold that we will use in our analysis will be identified through a data-driven approach formulated by Cattaneo et al.¹⁷ The baseline variables will be exploited to identify the largest window around the age 65 threshold within which there is no evidence that the patients vary significantly between groups in terms of those baseline variables. By identifying this window, an age range is identified across which the groups of patients can be said to be comparable at baseline. These patients are then used in the main analysis to estimate treatment effects. This method assumes that the baseline variables adequately account for differences in pre-intervention characteristics within this window that might affect outcomes and vary by age. This assumption implies that the outcomes are conditionally independent of the baseline variables.

The window will be identified by first conducting tests of mean differences in the baseline variables at the narrowest window – ie 1 week either side of the age 65 threshold, and with a minimum of 10 observations (patients) per group. Each baseline variable will be tested and the smallest resulting p-value reported. The window will then be increased by 1 week either side of the threshold and the process repeated. The maximum window used in the main analysis will be the smaller of (a) the one immediately prior to the window where a statistically significant

difference between groups is first identified, or (b) the one where the sample size achieved should comfortably identify a statistically significant difference in the outcome based on power calculations*.

Although we believe that the window will be determined by (a), the criterion in (b) will ensure that any potential for unobserved confounding caused by the use of a very wide window is limited.

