Where relevant, we will make use of the Benjamini-Hochberg procedure²⁸ to adjust for the increase in the false discovery rate (type 1 errors) due to multiple testing.²³

Descriptive analyses of patient flow

For context, we will create a flow diagram based on the CONSORT standard²⁹ of how patients move between receiving a COVID-19 positive test, are onboarded and use hospital services. This will help visualise some of the implicit decisions that we make, for example by showing the number (and percentage) of patients that were first enrolled following A&E. We will also check and document the number (and percentage) of patients who were onboarded without a COVID-19 positive test, and therefore excluded from our analysis.

We will also use the onboarding data to understand the enrolled population: the number of patients who are enrolled due to age, CEV status, both or neither. Likewise, we will consider these categories in those patients who were not enrolled. As long as these patients are flagged as CEV in the GDPDR data, we will be able to identify these patients.

Subgroup analyses

As care home residents will have access to support to use the pulse oximeters and record measurements correctly, care home residency may act as an effect modifier. However, as it is possible that many care home residents below 65 years of age will also be eligible for CO@h (eg because of learning disabilities, according to the SOP) it will probably not be possible to do a subgroup analysis on care home residents using the RDD method and we may exclude these patients from the study cohort. If they are not excluded, we may still run an RDD in the subgroup of patients not in care homes, which would potentially allow for an analysis with a sharper discontinuity at age 65.

Given the inequalities that COVID-19 has exposed, it is important to understand whether technologies such as the use of remote pulse oximeters are helping the communities worst affected by the pandemic. If the study is sufficiently powered, we will estimate the intervention effect in patients who live in the most socio-economically deprived areas. We could look at either the most deprived IMD quintile or the aggregate of the two most deprived IMD quintiles. We may also estimate the intervention effect in patients of different ethnic groups

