COVID-19 vaccinations commenced in December 2020, starting with older care home residents and care home staff, then moving down the priority list. By 15 February 2021, all patients aged 70 and over or CEV should have been offered a vaccination. If vaccinations are effective in stopping people getting COVID-19, this will affect the size of our cohorts, rather than confound our results. However, if vaccinated patients can still get COVID-19 but with milder symptoms (and therefore less likely to require hospital care), this could confound our analysis. We will be provided with information on the roll-out of the vaccinations and will aim to end the study period before or at the point vaccinations start being routinely provided to patients aged 65–70. This will ensure that there is limited confounding close to the threshold. The study period can be, if appropriate, tailored to different areas depending on local vaccination rates.

Some of the outcomes of this study may be difficult to interpret, either because of opposing mechanisms at play or because of other interventions, such as CVWs. However, our primary outcomes, relating to critical care and mortality, are expected to be easier to interpret. The qualitative analysis may also be able to provide contextual information to help interpret our results.

The aim of CVWs is to discharge patients earlier to alleviate the current pressures in hospitals. This could therefore impact on one of the outcomes of the CO@h evaluation: hospital bed days. As we will not have access to data on virtual ward enrolment, we are not able to assess whether CVWs affect patients' total hospital bed days in the CO@h intervention or control groups differently, and therefore whether any difference – or lack of difference – in outcomes is due to CO@h or CVWs. Although patients who are discharged early with CVWs may in general have different characteristics, eg in age, from those that are not, we do not expect a

discontinuity at age 65. Likewise, while CVWs may be used more in areas where there is the most pressure on hospital beds, by virtue of 'treated' and 'control' patients being found within the same areas and hospitals, we do not expect this to cause any bias in our analyses.

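### Whether care home residents stay in the main analysis depends only on their onboarding pattern, and the vaccination safeguard, tied to ages 65–70, does not cover a group vaccinated first from December 2020

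*SAP*

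**What the plan says.** The patient-level exclusions in Study cohort list CEV patients without qualification, but care homes only as "Potential additional exclusion: patients living in care homes". The text below the list gives the rule: residents are examined by age and onboarding status and, "if no age-related discontinuity is identified, will also be excluded from the analysis". Item 4 of the diagnostic checks repeats it for CEV and care home patients: "exclude these patients from the analysis if there is no discontinuity to exploit at age 65". Neither place mentions vaccination.

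On vaccination, the Background says: "The roll-out of COVID-19 vaccinations in England started on 8 December 2020". The first priority group is "Residents in a care home for older adults and their carers". Strengths and limitations agrees: "COVID-19 vaccinations commenced in December 2020, starting with older care home residents and care home staff, then moving down the priority list". That section accepts that milder disease in vaccinated patients could confound the results. Its remedy is to end the study period by the time people aged 65–70 are routinely vaccinated. The study period section expects the earliest start at the beginning of December 2020 and usable data until at least 15 February 2021, subject to checks.

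Subgroup analyses notes that "it is possible that many care home residents below 65 years of age will also be eligible for CO@h". If residents are kept, it says a non-care-home RDD may be run, and the reason given is a sharper discontinuity.

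**The concern.** The safeguard reasons by age. People aged 70 or over are vaccinated first, the window is expected to reach about five years either side of 65, and so the window should be largely unvaccinated until mid-February. Care home residents do not fit that reasoning, because their priority came from where they lived. Any who remain in the cohort could have been vaccinated during almost the whole study period, well before the age-based trigger acts.

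This matters only if vaccination among residents differs between the two sides of 65. The priority group covers homes for older adults, and the SAP gives learning disability as one reason why residents under 65 may be eligible for CO@h. It is therefore plausible that vaccinated residents sit more on the older side. Deaths and critical care use would then be lower there for a reason other than CO@h, and the estimate would favour the programme on its primary outcomes.

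**Working it through.** **Timing**
- Roll-out starts 8 December 2020, with older care home residents first.
- Earliest expected study start: beginning of December 2020.
- The end-date trigger is routine vaccination at ages 65–70, which the SAP expects no earlier than about 15 February 2021.
- Care home vaccination therefore runs inside nearly all of the study period, and the trigger does not act on it.

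**Would the planned analyses show it?**
- Baseline variables: neither care home residence nor vaccination is among the nine listed. Both are therefore also absent from the placebo outcomes, which use the same list.
- Main analysis: a difference in means with polynomial order zero and no covariates. A gradual excess of vaccinated residents on the older side is enough to enter the estimate; a step at 65 is not required.
- Sources of data: a care home flag is listed. Patient-level vaccination data are not; only information on roll-out is promised.
- Placebo study period: it precedes CO@h in each CCG and is run only if the sharp analysis is significant.
- Non-care-home analysis: optional.

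**Size.** The SAP gives no figure for this bias, so there is none to reproduce. Table 1 supplies the yardstick. At baseline risk p1 = 1% and relative risk 75%, p2 = 0.75% and the mean is 0.875%. The pooled-variance formula, n per group = [1.96·√(2·0.00875·0.99125) + 0.842·√(0.01·0.99 + 0.0075·0.9925)]² / 0.0025², gives 21,784 per group and 43,568 in total, as printed. The effect sought in that cell is 0.25 percentage points under full compliance.

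Bias on the eligibility scale = c × r × d × v. All inputs are assumptions:
- c, residents' share of positive patients in the window: 0.5–2%
- r, 28-day death risk in unvaccinated residents: 15%
- d, coverage gap among residents across 65: 0–40 points
- v, reduction in death risk from vaccination: 60%

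Per complier, divide by the enrolment jump, assumed to be 20 points.

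| c | d | Eligibility scale (points) | Per complier (points) |
|---|---|---|---|
| any | 0 | 0 | 0 |
| 0.5% | 20 | 0.005 × 0.15 × 0.2 × 0.6 = 0.009 | 0.045 |
| 1% | 20 | 0.01 × 0.15 × 0.2 × 0.6 = 0.018 | 0.09 |
| 1% | 40 | 0.01 × 0.15 × 0.4 × 0.6 = 0.036 | 0.18 |
| 2% | 40 | 0.02 × 0.15 × 0.4 × 0.6 = 0.072 | 0.36 |

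The inputs held fixed also matter. With c = 2% and d = 40 points, moving from r = 5%, v = 30% to r = 20%, v = 80% takes the eligibility-scale bias from 0.012 to 0.128 points. A 10-point enrolment jump doubles each per-complier figure in the table.

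**The case against.** The strongest objection is that the decisive step is not in the SAP. Priority went by type of home. A 64-year-old and a 66-year-old in the same home for older adults are both in group 1, and if coverage is alike across 65 there is no bias. A reader might infer that residents' vaccination jumps at 65, or that confounding is established. The SAP supports neither; at most it makes an age gradient in type of home plausible. A reader might also say that no end date yields an unvaccinated care home group. The first days of December precede the roll-out, and in any case the design needs comparability across 65, not an unvaccinated group.

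Second, the SAP treats the affected branch as unlikely. If many residents under 65 are eligible anyway, no jump appears and the existing rule removes them. CEV residents are already excluded, so only the non-CEV remainder is at issue.

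Third, partial protections exist: roll-out monitoring, area-specific end dates, reruns in smaller windows (which would shrink a gradient) and Rosenbaum bounds. Vaccination that prevents infection would also lower the number of vaccinated residents among positive tests.

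All of this stands as a limit on likelihood and size. It does not close the gap: the retention rule ignores vaccination, the end-date trigger acts on a different group, and none of these protections is specific to care homes or would identify them as the source of a shift.

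**Conclusion.** The point holds as a minor tightening. The plan could keep in its main analysis a group that its vaccination safeguard does not reach, and could not readily recognise the result. Whether bias follows depends on a coverage difference across 65 that the SAP does not report. Under the main assumptions the spurious reduction in deaths is 0 to 0.072 points on the eligibility scale, or 0 to 0.36 per complier at a 20-point jump. The yardstick is 0.25 points, so only the upper end of that range, with a 2% share and a 40-point gap, exceeds the effect sought. Zero is a credible value, and no input comes from the SAP, so these figures show what is possible and are not an estimate.

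**What to change.** In the Study cohort exclusion list, the paragraph below it and item 4 of the diagnostic checks, replace the conditional rule with a fixed exclusion of care home residents from the main analysis, using the care home flag already listed under Sources of data. Keep the check of residents' onboarding by age as description. If wanted, add a sensitivity analysis that includes residents.

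The minimum alternative is to make the non-care-home analysis in Subgroup analyses mandatory for the primary outcomes whenever residents are retained, and to give vaccination as a reason for it.

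The cost is a change of wording, a probably small loss of patients, and no inference for residents. Strengths and limitations already accepts that last limit as a possible consequence.
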